6.0 TRIAL FLOW CHART

6.1 Study Flow Chart

Trial Period:	Screening Phase		Treatment Cycles								treatment end
			1	2	3	4	to be repeated until week 105				
Treatment Cycle/Title:	Pre study	screening (Visit 2)	5	6	7	8	Safety Follow-up				
Scheduling Window (Days):		-14 to -1		± 5	± 5	± 5	± 5	± 5	± 5	± 5	days post discon
Informed Consent	X										
Inclusion/Exclusion Criteria	X	X									
Demographics and Medical History	X										
prior/concomitant medication review	X										
Review Adverse Events		X	X	X	X	X	X	X	X	X	X
Physical Examination		X	X	X	X	X----as per standard of care-----X					
Vital Signs and Weight		X									
ECOG Performance Status		X									
Pregnancy Test (if indicated)		X									
HIV, active TB and acute hepatitis panel (if indicated)		X									
PT/PTT		X									
CBC with Differential		X	X	X	X	X-----as per standard of care----X					
Comprehensive Serum Chemistry Panel		X	X	X	X	X-----as per standard of care----X					
T3, FT4 and TSH		X	X	X	X	X	X	X	X	X	
Cardiac function (EKG/ECG)		X									
Serum Troponin I, BNP		X		X							
Pembrolizumab			X	X	X	X ^c	X	X	X	X	
p53MVA			X	X	X						
Tumor Imaging (CT or PET/CT)	X				X			X--every 9 weeks--X			
CA-125		X	X	X	X	X	X	X	X	X	
Immunologic Blood Collection ^b			X	X	X	X		*X	*X	*X	

Study Chart Notes: Baseline evaluations must be conducted no more than 14 days before treatment start, except imaging which are permissible up to 30 days prior to initiation of therapy. All treatments/evaluations during/after the treatment phase may be +/- 5 days. *At the discretion of the PI. ^aImaging scans must be obtained prior to cycle 4 of therapy +/- 5 days. Subsequent restaging scans will be obtained after every 3 cycles of treatment. +/- 5 days. ^bAll blood specimens to be collected prior to administration of study agents. Patients with a hemoglobin (Hgb) level < 9g/dL will not undergo further immunologic phlebotomy until the Hgb level has been documented to rise above 9g/dL. ^cAfter completion of the three combined doses of p53MVA + PEM, continued administration of PEM as a single agent may continue up to week 49 (first course). ^dPatients completing Week 49 treatment will have an end of study visit, 1-3 weeks after the last dose of PEM. See Section 5.2.3. on 'Second course' of Pembrolizumab.

7.0 TRIAL PROCEDURES

7.1 Trial Procedures

The Trial Flow Chart - Section 6.0 summarizes the trial procedures to be performed at each visit. Individual trial procedures are described in detail below. It may be necessary to perform these procedures at unscheduled time points if deemed clinically necessary by the investigator.

Furthermore, additional evaluations/testing may be deemed necessary by the Sponsor and/or Merck for reasons related to participant safety. In some cases, such evaluation/testing may be potentially sensitive in nature (e.g., HIV, Hepatitis C, etc.), and thus local regulations may require that additional informed consent be obtained from the participant. In these cases, such evaluations/testing will be performed in accordance with those regulations.

7.1.1 Administrative Procedures

7.1.1.1 Informed Consent

The Investigator must obtain documented consent from each potential participant prior to participating in a clinical trial.

7.1.1.1.1 General Informed Consent

Consent must be documented by the participant's dated signature or by the participant's legally acceptable representative's dated signature on a consent form along with the dated signature of the person conducting the consent discussion.

A copy of the signed and dated consent form should be given to the participant before participation in the trial.

The initial informed consent form, any subsequent revised written informed consent form and any written information provided to the participant must receive the IRB approval in advance of use. The participant or his/her legally acceptable representative should be informed in a timely manner if new information becomes available that may be relevant to the participant's willingness to continue participation in the trial. The communication of this information will be provided and documented via a revised consent form or addendum to the original consent form that captures the participant's dated signature or by the participant's legally acceptable representative's dated signature.

Specifics about a trial and the trial population will be added to the consent form template at the protocol level.

The informed consent will adhere to IRB requirements, applicable laws and regulations and Sponsor requirements.

7.1.1.2 Inclusion/Exclusion Criteria

All inclusion and exclusion criteria will be reviewed by the investigator or qualified designee to ensure that the participant qualifies for the trial.

7.1.1.3 Medical History

A medical history will be obtained by the investigator or qualified designee. Medical history will include all active conditions, and any condition diagnosed within the prior 10 years that are considered to be clinically significant by the Investigator. Details regarding the disease for which the participant has enrolled in this study will be recorded separately and not listed as medical history.

7.1.1.4 Prior and Concomitant Medications Review

7.1.1.4.1 Prior Medications

The investigator or qualified designee will review prior medication use, including any protocol-specified washout requirement, and record prior medication taken by the participant within 28 days before starting the trial. Treatment for the disease for which the participant has enrolled in this study will be recorded separately and not listed as a prior medication.

7.1.1.4.2 Concomitant Medications

The investigator or qualified designee will record medication, if any, taken by the participant during the trial. All medications related to reportable SAEs and ECIs should be recorded as defined in Section 7.2.

7.1.1.5 Disease Details and Treatments

7.1.1.5.1 Disease Details

The investigator or qualified designee will obtain prior and current details regarding disease status.

7.1.1.5.2 Prior Treatment Details

The investigator or qualified designee will review all prior cancer treatments including systemic treatments, radiation and surgeries.

7.1.1.5.3 Subsequent Anti-Cancer Therapy Status

The investigator or qualified designee will review all new anti-neoplastic therapy initiated after the last dose of trial treatment. If a participant initiates a new anti-cancer therapy within 30 days after the last dose of trial treatment, the 30 day Safety Follow-up visit must occur before the first dose of the new therapy. Once new anti-cancer therapy has been initiated the participant will move into survival follow-up, according to COH standard practice.

7.1.1.6 Patient Registration

Eligible subjects must be registered with the Clinical Trials Office (CTO) **prior** to start of protocol therapy. Issues that would cause treatment delays should be discussed with the Principal Investigator. If a subject does not receive protocol therapy following registration, the subject's registration on the study may be canceled after discussion with the PI. The CTO should be notified of cancellations as soon as possible.

Once a patient has been identified, the signed informed consent has been obtained, all pretreatment evaluations have been performed, and subject's eligibility has been confirmed, a subject will be registered on study.

To register a subject, the treating physician should contact the protocol nurse or the responsible Clinical Research Coordinator (CRC) in the Clinical Trial Office (CTO) to complete the eligibility checklist.

The protocol nurse or CRC will **complete** eligibility and enroll patient to trial.

7.1.2 Clinical Assessments

The following laboratory tests will be conducted at baseline and during the treatment phase according to the study chart:

- a. Complete blood count with platelet count and differential
- b. Comprehensive metabolic panel
- c. Urine for pregnancy test where appropriate
- d. Blood for immune studies which will be processed and stored by [name] Lab. PBMC will be separated from heparinized blood by standard density gradient centrifugation and analyzed immediately, or cryopreserved for future analysis.
- e. Serum Troponin (I) and B-type natriuretic peptide (BNP)
- f. Immuno-histochemistry staining for the primary ligand of PD-1 (PDL-1)
- g. CA-125 tumor marker

7.1.2.1 Adverse Event (AE) Monitoring

The investigator or qualified designee **be responsible** for determining the event name, assessing the severity (i.e., grade), expectedness, and attribution of all adverse events as applicable per the City of Hope Clinical Research Adverse Event and Unanticipated Problem policy. Adverse events will be characterized using the descriptions and grading scales found in the most recent version of the NCI CTCAE Version 5.0 (see Appendix 2). Toxicities will be characterized in terms regarding seriousness, causality, toxicity grading, and action taken with regard to trial treatment.

Please refer to section 7.2 for detailed information regarding the assessment and recording of AEs.

7.1.2.2 Physical Exam

The investigator or qualified designee will perform a complete physical exam during the screening period. Clinically significant abnormal findings should be recorded as medical history. A full physical exam should be performed during the study according to standard of care.

7.1.2.3 Vital Signs

The investigator or qualified designee will take vital signs at screening, prior to the administration of each dose of trial treatment and at treatment discontinuation as specified in the Trial Flow Chart (Section 6.0). Vital signs should include temperature, pulse, respiratory rate, weight and blood pressure. Height will be measured at screening only.

7.1.2.4 Eastern Cooperative Oncology Group (ECOG) Performance Scale

The investigator or qualified designee will assess ECOG status (see Appendix 1) during eligibility screening.

7.1.2.5 Tumor Imaging and Assessment of Disease

Clinical response will be assessed by modified irRECIST criteria. Conventional RECIST criteria for measuring responses to cytotoxic agents are not optimal for immunotherapies which do not act directly on the tumor, and reductions in disease burden may take many months to occur. Therefore improved overall survival (OS) can result without improved progression free survival/time to progression (PFS/TTP). Hence, we will employ *Immune-related response criteria* (irRECIST, irRC) which are adapted from WHO response criteria are being employed for immunotherapy trials [52], shown below:

New, measurable lesions (i.e., $\geq 5 \times 5$ mm)	Incorporated into tumor burden
New, non measurable lesions (i.e., $< 5 \times 5$ mm)	Do not define progression (but preclude irCR)
Non-index lesions	Contribute to defining irCR (complete disappearance required)
CR	Disappearance of all lesions, 2 consecutive observations, ≥ 4 wks apart
PR	$\geq 50\%$ decrease in tumor burden from baseline, 2 consecutive observations, ≥ 4 wks apart
SD	50% decrease in tumor burden from baseline cannot be established, nor 25% increase compared with nadir
PD	At least 25% increase in tumor burden compared with nadir (at any single time point) in two consecutive observations at least 4 wk apart

Decreased tumor volume will be assessed relative to baseline, including measurable lesions $> 5 \times 5$ mm. Only index and measurable new lesions are taken into account in irRC (in contrast to conventional WHO criteria which do not require the measurement of new lesions, nor do they include new lesion measurements in the characterization of evolving tumor burden).

At the baseline tumor assessment, the sum of the products of the two largest perpendicular diameters (SPD) of all index lesions (five lesions per organ, up to 10 visceral lesions and five cutaneous index lesions) is calculated. At each subsequent tumor assessment the SPD of the index lesions and of new, measurable lesions ($\geq 5 \times 5$ mm; up to 5 new lesions per organ: 5 new cutaneous lesions and 10 visceral lesions) are added together to provide the total tumor burden: Tumor Burden = SPD index lesions + SPD new, measurable lesions

Target Lesions

All measurable lesions up to a maximum of 2 lesions per organ and 5 lesions in total, representative of all involved organs, should be identified as **target lesions** and recorded and measured at baseline. Target lesions should be selected on the basis of their size (lesions with the longest diameter), be representative of all involved organs, but in addition should be those that lend themselves to reproducible repeated measurements. It may be the case that the largest lesion does not lend itself to reproducible measurement in which circumstance the next largest lesion which can be measured reproducibly should be selected. A sum of the diameters (longest for non-nodal lesions, short axis

for nodal lesions) for all target lesions will be calculated and reported as the baseline sum diameters. If lymph nodes are to be included in the sum, then only the short axis is added into the sum. The baseline sum diameters will be used as reference to further characterize any objective tumor regression in the measurable dimension of the disease.

Percentage changes in tumor burden per assessment time point describe the size and growth kinetics of both conventional and new, measurable lesions as they appear. At each tumor assessment, the response in index and new, measurable lesions is defined based on the change in tumor burden (after ruling out irPD). Decreases in tumor burden must be assessed relative to baseline measurements (i.e. the SPD of all index lesions at screening).

Non-Target Lesions

All other lesions (or sites of disease) including any measurable lesions over and above the 5 target lesions should be identified as **non-target lesions** and should also be recorded at baseline. Measurements of these lesions are not required, but the presence, absence, or unequivocal progression of each should be noted throughout follow-up.

Metastatic Bone Lesions

Disease progression is considered if a minimum of 2 new lesions is observed on bone scan. New lesions seen by the end of the first response assessment (with the first re-staging bone scan) may represent disease that was not detected on the pre-study scan, and a confirmatory scan will be required at the next scheduled re-staging bone scan unless clinically not indicated. If confirmed, progression should be dated by the initial time when the lesions are first detected. If new lesions are seen after the first assessment, but no additional lesions are seen on confirmatory scans, the scans from post-first assessment would serve as the baseline scan to evaluate for disease progression.

Clinical Lesions

Clinical lesions will only be considered measurable when they are superficial e.g. palpable lymph nodes.

Measurable Disease

All measurements will be taken and recorded in metric notation using a ruler or calipers. All baseline evaluations will be performed as close as possible to the beginning of treatment. The same method of assessment will be used to characterize each identified and reported lesion at baseline and during follow-up. Imaging-based evaluation is preferable unless the lesion(s) being followed cannot be imaged but are assessable by clinical exam.

Duration of Response

The duration of overall response will be measured from the time measurement criteria are met for CR, PR or SD until the first date that recurrent or progressive disease is documented.

Progression-Free Survival (PFS)

PFS is defined as the duration of time from start of treatment to time of progression or death, whichever occurs first.

Overall Survival (OS)

OS will be determined for each patient with time origin at the start of the treatment until death. Every effort will be made to follow patients for survival after they discontinue the study.

Conventional CT and PET/CT: both CT and PET/CT will be acceptable for measuring baseline and post treatment disease burden.

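### Section 7.1.2.5 gives two lesion-selection and measurement rules for the primary response endpoint that cannot both be followed

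*Combined protocol and SAP*

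**What the plan says.** Sections 4.2.3.1 and 8.1 make response rate (CR plus PR) the primary endpoint. Section 4.2.3.1 names irRECIST and points to Section 7.1.2.5, which contains two descriptions.

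- **Opening text and table.** The baseline SPD covers all index lesions: "five lesions per organ, up to 10 visceral lesions and five cutaneous index lesions". At later scans, "Tumor Burden = SPD index lesions + SPD new, measurable lesions". PR needs at least a 50% "decrease in tumor burden from baseline, 2 consecutive observations", 4 weeks or more apart. PD needs at least a 25% rise from nadir, confirmed over a similar interval. The section adds: "Only index and measurable new lesions are taken into account in irRC".
- **Target Lesions and Non-Target Lesions.** The lesions to be measured are "All measurable lesions up to a maximum of 2 lesions per organ and 5 lesions in total, representative of all involved organs". One diameter per lesion is summed (short axis for nodes), and "The baseline sum diameters will be used as reference to further characterize any objective tumor regression". Measurable lesions beyond these five become non-target and need not be measured. Yet the Target Lesions text also says that decreases must be judged against the screening SPD of all index lesions.

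Section 5.1.1 defines measurable disease in at least one dimension, with the longest to be recorded. Section 8.2 continues past 17 patients if at least 2 respond and needs at least 5 responders of 28.

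On clinical benefit, Section 3.2 lists CR and PR lasting over 6 months, without SD. Sections 4.2.3, 4.2.3.1 and 8.1 give CR, PR and SD with a 6-month condition. The one calculation sentence, in 8.1, counts CR, PR or SD with no duration.

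**The concern.** The two descriptions differ in how many lesions count, in whether one or two dimensions are used, and in which lesions are measured at all. No sentence says how target lesions relate to index lesions, and no percentage threshold is given for a sum of diameters. A site that follows the Target Lesions text may lack the second diameter, or whole lesions, that SPD tumor burden requires.

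PR and PD calls feed the response rate and PFS. The response rules turn on very few patients. Section 8.2 lets the final determination weigh the totality of clinical endpoints, but the stage-1 rule carries no such qualifier.

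**Working it through.** **1. The plan's design figures (Section 8.2).** Inputs: rates 8% and 25%; n1 = 17, continue if X1 ≥ 2; N = 28, success if the total is ≥ 5.

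P(success) = Σ over x ≥ 2 of P(X1 = x) × P(Bin(11, p) ≥ 5 − x).

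- At p = 0.25: 0.852 (plan: 85% power).
- At p = 0.08: 0.065, within the stated 8%.
- Early stopping at p = 0.08: P(X1 ≤ 1) = 0.601 (plan: 60%).

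The sample size is sound. The question is who counts as a responder.

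**2. Effect of the lesion cap alone, with SPD used throughout.** Assumptions (mine, since the documents give no lesion data): round lesions, all in one organ, no new lesions, so SPD = Σ d². The index rule takes all five lesions; the target cap takes the two largest.

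| Diameters, mm | SPD, five lesions | SPD, two lesions |
|---|---|---|
| 30, 30, 28, 28, 28 → 24, 24, 16, 16, 16 | 4152 → 1920 = -53.8% (PR if confirmed) | 1800 → 1152 = -36.0% (not PR) |
| 40, 30, 25, 25, 25 → 18, 14, 25, 25, 25 | 4375 → 2395 = -45.3% (not PR) | 2500 → 520 = -79.2% (PR if confirmed) |

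The cap can therefore remove or create a PR without any assumption about a diameter threshold.

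**3. Sensitivity of the stage-1 decision.** One changed call can reverse it only if X1 is exactly 1 (needs an upgrade) or exactly 2 (needs a downgrade).

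- p = 0.08: 0.358 + 0.249 = 0.607.
- p = 0.25: 0.043 + 0.114 = 0.156 before rounding of the terms.

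These are upper bounds on the chance that one reclassified patient reverses the decision. They do not give the chance that such a patient exists or is moved in the direction that matters.

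**4. Clinical benefit.** Under Section 6.1, scans fall before cycle 4 and then every three 3-week cycles, about days 63, 126 and 189. For SD at the first two scans and PD at the third, duration is 189 days from start of treatment, or 189 − 63 = 126 days from first meeting SD criteria. Six months is about 182.6 days, so the start point can decide the result.

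**The case against.** The strongest reply is that the metric is not really open. Every response percentage attaches to tumor burden, which is defined once, as SPD; the Target Lesions text itself returns to SPD; and the sum of diameters only helps to characterize regression. That stands for the metric. It does not settle the cap or the instruction that other lesions need not be measured.

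The effect is also limited. The lesion sets coincide in patients with no more than 2 measurable lesions per organ and 5 in total. CR requires all lesions to disappear, so neither cap nor metric alters it. Both limits stand.

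A reader might infer three stronger points that the documents do not support.

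- **That even one-lesion patients would be called differently.** A round lesion going from 40 to 28 mm is -51.0% by SPD (1600 → 784) and -30.0% by diameter; one going from 40 to 45 mm is +26.6% (1600 → 2025) and +12.5%. The calls differ only if 50% and 25% are applied to diameters, which the plan nowhere says. With geometrically equivalent cut-offs, 1 − √0.5 = 29.3% and √1.25 − 1 = 11.8%, they agree.
- **That power drops by a known amount.** If 10%, 20% or 30% of SPD responders were missed, success at a true 25% would fall to 77%, 67% or 54%. Those shares have no basis in the documents and allow only downgrades, whereas the second illustration is an upgrade.
- **That SPD must be the sole rule for every purpose.** Section 4.2.3.1 names irRECIST, Section 7.1.2.5 uses irRECIST and irRC as one, and Section 5.1.1 records one dimension. The sponsor's intention cannot be settled from this text.

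On clinical benefit, the calculation sentence in 8.1 follows a definition that has the 6-month condition and may simply sum its parts, and the Duration of Response text gives a start point that covers SD. That makes the point minor, but 3.2 still omits SD and nothing ties that start point to the 6 months.

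**Conclusion.** The concern holds as a conflict over lesion selection and measurement for the primary endpoint. The text is wrong as written, not merely short of detail, and needs correcting. SPD is the better-supported response metric, but data collected under the Target Lesions text may not permit it.

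The cap can change PR calls both ways, though only in patients above 2 measurable lesions in an organ or 5 overall. The shift in response rate cannot be computed, because lesion counts and sizes are not given; the illustrations show that reversals are possible, not how often they occur. At most, one changed call could reverse stage 1 with probability 61% at a true rate of 8% and 16% at 25%. The sample size and stated operating characteristics are unaffected. The clinical-benefit wording is a minor, separate correction.

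**What to change.** Reconcile the opening of Section 7.1.2.5 with its Target and Non-Target Lesions text, the irRECIST naming in 4.2.3.1 and the one-dimensional measurability text in 5.1.1. State one lesion set, one metric and thresholds written for that metric, and require every lesion in the set to be measured at each scan. For the response-rate endpoint the least disruptive route is to align the target-lesion terms and cap with the index-lesion rule, since thresholds exist only for SPD. Progression also governs stopping of treatment (Sections 5.4 and 7.1.5.2), so the sponsor must confirm which progression rule applies there; this review does not choose one.

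For clinical benefit, use the definition in 4.2.3, 4.2.3.1 and 8.1 throughout: add SD in 3.2, restore the 6-month condition in the 8.1 calculation sentence, and say whether the Duration of Response start point applies.

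The cost is protocol and SAP wording, with no new patients or scans. If the index-lesion rule is kept, some patients will have more lesions to measure per scan, and stored images must be re-measured wherever the smaller cap or single diameters were used.
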